1.1. Objectives

Our primary aim in this pilot project is to test the feasibility, acceptability and impact of a brief behavioral treatment for depression (Engage) combined with video social support (PRISM 2.0) among socially isolated/lonely case management clients who endorse depressive symptoms. Secondarily, we will assess technology-related outcomes.

We plan to recruit 50 subjects based on a proposed recruitment of at least 3 subjects per month (17 months). Eligible participants will be offered the combination of Engage and Prism 2.0, called Engage-Prism.

1.2. Hypotheses / Research Questions

We hypothesize that the intervention will be acceptable by participants and that it will improve social connection, perceived social support, and reduce loneliness and depressive symptoms.

2. Background and Significance

Older adults who are homebound are socially disconnected with high rates of loneliness and depression. Social isolation places individuals at risk of all-cause mobility and mortality (Holt-Lunstad & Hawley 2016) including suicidal attempts (Calati et al., 2019). In the Health and Retirement study social disconnectedness is associated with 5% risk of falls, and social isolation combined with loneliness is associated with a 33% increase in falls (Quach & Burr, 2020). In a sample of 1,885 homebound and semi-homebound older adults from the National Health and Aging Trends Study (NHATS) 15.62% scored above the suicide risk cutoff, 23.73% of homebound older adults reported a history of suicidal ideation or behavior, 65 adults in this sample (13.18%) indicated the possibility of attempting suicide in the future (Xiang & Brooks, 2017). Social isolation and depression may be bidirectional (Santini et al, Lancet 2020). Aging services providers are not trained to distinguish loneliness, depression and disconnection making links to appropriate services challenging (Choi NG, Sirey JA, Bruce ML, 2013).

Brief behavioral interventions have shown an increase in social interaction, a decrease in loneliness, depression and disability (Choi and Bruce, 2020). Engage is a brief therapy designed to offer a structured, stepped approach and interventions to reduce barriers to increased engagement with rewarding activities to improve depression ([name] et al, 2020). The goal is to increase participation in meaningful activities. Recent research supports the importance of engagement in social interpersonal-individual predicting subsequent increases in behavioral activation and improvement of depression (Solomonov et al, 2019). Homebound older adults have limited social interaction given their restricted mobility and medical burden. Innovative steps to improve interactions have used technology to link clients who are homebound. In an intervention targeting social engagement with a technology intervention (PRISM 2.0), participants reported increased social support, decreased loneliness, increased feelings of well-being, more positive attitudes about computers, and gains in computer proficiency (Czaja et al., 2017). These gains were maintained improvements at 12 month follow-up.

3. Study Design and Methods

3.1 Overall Design

The study will include the following steps:

1. Referral from case management service, determination of eligibility, collection of informed consent
2. Baseline assessment and training with the Engage-Prism technology
3. 9 Engage sessions (1 per week) and use of the Prism platform (9 weeks total)
4. Brief interim assessments at 3 and 6 weeks
5. Post-therapy assessment and follow-up interview at week 9
6. Follow-up assessment at week 12

Details related to the questionnaires in the baseline and Week 9 assessment as well as the follow-up interview are described in the subsequent sections.

3.2 Baseline assessment/training, Engage sessions, technology use, post-study assessment and interview

3.2.1 Baseline assessment and training

Participants will be mailed the Prism technology or provided the technology in-person. Participants will be provided a tablet and trained in the utilization of Prism by a study team member and technology specialist. Trainings will occur virtually (via Zoom or telephone) or in-person. In-person training will be conducted by research assistants and occur in the participants' home as many are homebound. The determination for in-person versus virtual training will be based on the preference of the participant the research regulations of Weill Cornell Medicine pertaining to the on-going COVID-19 pandemic. Following the training, baseline questionnaire data will be collected with the study team member reading the questions aloud and marking the responses of the participant. Included questionnaires are described in the subsequent section.

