3.2.2 Questionnaires

Questionnaires collected during the baseline and study assessments include (attached to IRB application):

1. Hamilton Depression Rating Scale (HAMD) for depression severity
2. Behavioral Activation for Depression Scale (BADS) for behavioral activation*
3. Duke social interaction subscale – to assess social connection
4. Duke perceived support subscale – to assess perceived social support
5. UCLA 3-item scale – to assess loneliness
6. 12-item World Health Organization Disability Assessment Schedule (WHODAS 2.0)- to assess different domains of disability**

7. Technology readiness questionnaire (Jay & Willis, 1992)*
8. Mobile Device Proficiency Scale (MDPQ-16)
9. Computer tablet opinions questionnaire (Czaja et al., 2018)*
10. Demographics**
11. Client Satisfaction Questionnaire 3-item for therapy satisfaction
12. Intent to Participate – to assess intention to continue study

*Pre and post only (i.e. not at 3, 6 or 9 weeks)

**Pre only

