3.2.4. Prism system

Throughout the **12-week study**, participants will be given the Prism 2.0 system to use. Participants will be provided a tablet with internet access, pre-loaded with the Prism 2.0 software. The Prism software involves a suite of programs for improving the social support and interaction felt by older adults. Previous studies have demonstrated that Prism system reduces loneliness and increases perceived social support and computer proficiency (Czaja et al., 2017). Prism software includes: Internet browser access (with vetted links to sites such as NIHSeniorHealth.Gov), an annotated resource guide, a dynamic classroom feature, a calendar, a photo feature, E-mail, games, and online help. Clinicians will incorporate elements of the Prism system into therapy as appropriate, and participants will be instructed to use the Prism system at their leisure or as it pertains to their chosen “reward exposure” activities.

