4.3 Exclusion Criteria

1. Psychotic depression by SCID-V, i.e. presence of delusions
2. High suicide risk, i.e. intent or plan to attempt suicide in the near future
3. Presence of any Axis I psychiatric disorder or substance abuse other than unipolar major depression
4. History of psychiatric disorders, hypomania, are excluded
5. Acute or severe medical illness, i.e. delirium, metastatic cancer, decompensated cardiac, liver, or kidney failure, major surgery, stroke, or myocardial infarction during the three months prior to entry; or drugs often causing depression, e.g. steroids, reserpine, alpha-methyl-dopa, tamoxiphen, vincristine
6. Current involvement in psychotherapy
7. Cognitive impairment (i.e. telephone administered MoCA < 11)
8. Currently dwelling in non-community dwelling (e.g. prison, nursing home)
9. Hearing that would not allow participants to complete sessions with the RA/therapist
10. Vision impairment that would not allow the participant to use the study provided tablet
11. Inability to speak English
12. Aphasia interfering with communication
13. Literacy – assessed by reading a paragraph designed for those at 6th grade reading level

INSTRUMENTS	Administered by:	Screening	Baseline	Wk 3	Wk 6	Wk 9	Wk 12
Screening Assessment							
Demographic Questionnaire	Research Assistant (RA)	X	X				
Medication List	RA	X					
Health Information Questionnaire	RA	X					
Functional status (WHODAS 12-item)	RA		X			X	X
Telephone- MoCa	RA	X					
Dx, Depression Severity and Anhedonia							
Hamilton Depression Rating Scale (HAMD)	Research Assistant	X	X	X	X	X	X
Structured Clinical Interview for DSM -V	Clinician	X					
SCID Score Sheet	RA	X					
PHQ-9	Clinician						Weekly during clinician sessions
Behavioral Activation							
Behavioral Activation for Depression Scale (BADS)	RA		X	X	X	X	X
Social Connection and Loneliness							
Duke (social interaction and perceived support subscales)	RA		X	X	X	X	X
UCLA Loneliness Scale 3-item	RA		X	X	X	X	X
Technology							
Technology readiness questionnaire	RA		X			X	
Mobile Device Proficiency Scale (MDPQ-16)	RA		X			X	X
Computer Tablet Opinions Questionnaire	RA		X			X	
Other							
Client Satisfaction Questionnaire 3-item	RA			X	X	X	X

Intent to Participate	RA		X	X	X	X	

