4.4 Strategies for Recruitment and Retention

Case managers will inform the potential participants of the study and let them know that a study team member will contact them. Following referral by case management, eligible participants will be contacted by study staff via phone to provide the initial consent. Eligibility will be confirmed by the study personnel, and potential participants will be invited to participate in the study.

Subjects participating in this study will be compensated approximately \$25 for each research assessment (\$125 total) for completion of the study. Subjects will receive \$25 via check or gift card in the mail for remote visits. There is no charge or compensation for the weekly psychotherapy sessions.

If participants do not “log on” to the Prism system for 7 consecutive days, a study team member will call them to make sure they do not have questions, technical issues, or require re-training.

5. Registration Procedures

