6.1.2. Questionnaires (baseline and post-study)

Personnel conducting the study will verbally ask questions contained in the questionnaires described, and record the participants answers using pen/paper or electronic form. Study investigators will write the participant number on each questionnaire so questionnaires from the same participant can be matched. Assessments will be collected prior to the first Engage session and following the final Engage session.

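### The three technology scales are first read after Prism training, so any change from baseline leaves out whatever changed during that training

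*Protocol*

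**What the plan says.** Protocol section 3.2.1 describes delivery of the tablet, then training in Prism, and then the questionnaires: "Following the training, baseline questionnaire data will be collected with the study team member reading the questions aloud". It points to the list in section 3.2.2, where items 7 to 9 are the technology readiness questionnaire, the MDPQ-16 and the computer tablet opinions questionnaire.

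Three other places bear on timing. Step 2 of section 3.1 is "Baseline assessment and training with the Engage-Prism technology". Section 6.1.2 says "Assessments will be collected prior to the first Engage session and following the final Engage session". The schedule of instruments after section 4.3 gives the three technology scales, including the row "Computer Tablet Opinions Questionnaire", their first mark at Baseline.

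Section 1.1 makes technology-related outcomes the secondary aim. The Data Analysis part of section 6.1 plans hypothesis tests on baseline, interim and post-study assessments. The SAP replaces these with descriptive statistics because few subjects completed. Neither text mentions that baseline follows training.

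**The concern.** Training is part of delivering Prism, and it is the step aimed most directly at what these scales measure. The protocol itself links the system to proficiency: "Previous studies have demonstrated that Prism system reduces loneliness and increases perceived social support and computer proficiency". Its background section also credits an earlier Prism study with more positive attitudes about computers.

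A baseline read after training cannot represent the untrained participant. A reader of the results would naturally take a pre-post difference on the MDPQ-16, say, as the change that came with the whole package. Under the written plan it is the change after training only. The untrained value cannot be recovered later for anyone whose baseline followed training.

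**Working it through.** The plan states no figure on this point, so the check compares the timing statements with the schedule.

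**Step 1: what order is stated?**
- Section 3.2.1, body text: questionnaires follow training. This is an explicit sequence.
- Section 3.1, step 2, and the heading of section 3.2.1: both name baseline assessment before training, but as one combined step with no order inside it.
- Section 6.1.2: the anchor is the first Engage session, not Prism training. A post-training baseline satisfies it.

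Section 3.2.1 is therefore the only explicit order, and nothing states the opposite.

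**Step 2: is an earlier reading planned?** Marks in the schedule (Weeks 3 and 6 left out):

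| Scale | Screening | Baseline | Wk 9 | Wk 12 |
|---|---|---|---|---|
| Technology readiness | – | X | X | – |
| MDPQ-16 | – | X | X | X |
| Tablet opinions | – | X | X | – |
| HAM-D, for contrast | X | X | X | X |

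The HAM-D has a screening value as well as a baseline. Of the technology scales, 0 of 3 have a mark before Baseline, and no other section plans one.

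**Step 3: what does a change score contain?** For each scale:

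untrained-to-follow-up change = (post-training baseline − untrained value) + (follow-up − post-training baseline)

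The plan observes only the second term. That term still includes later gains, because the tablet is kept for the whole study ("participants will be given the Prism 2.0 system to use") and because a participant who has not logged on for 7 consecutive days is contacted: "a study team member will call them to make sure they do not have questions, technical issues, or require re-training". The first term is missing whether the second is tested or simply averaged, so the SAP's move to descriptive statistics leaves the issue where it was.

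**Step 4: how large is the first term?** The documents give no training effect, no expected change and no standard deviation for these scales. Training could raise self-rated proficiency. It could also expose difficulties and lower self-ratings. Neither size nor sign can be derived.

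**The case against.** The strongest reply is that nothing is lost because nothing was promised. No document defines a technology outcome as change from an untrained state. The hypotheses in section 1.2 name no technology scale. The only technology-specific analysis in the protocol concerns utilization. The SAP gives means and standard deviations as examples and commits to no change score. A post-training baseline is also a coherent reference for change during the weeks of Prism use. All of this stands, and it keeps the point minor. It does not remove the need for a label: the protocol nowhere says that a post-training reference was intended, and a reader will not assume one.

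A second reply is that the Screening column is an unreliable witness. Section 4.2 uses the UCLA and Duke measures for eligibility, yet neither has a Screening mark. A blank cell is therefore weaker evidence than it looks. This also stands, but no section positively plans an earlier technology reading.

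A third is that a written order is not conduct. Staff may have taken baseline first, as the wording of section 3.1 would allow. That is why the remedy for collected data begins with the records.

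It might also be said that training must come first so that participants can respond. This fails, because staff read the questions aloud and mark the answers.

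**Conclusion.** The point holds as a minor design and labelling issue. As planned, all three technology scales start from a post-training value, and any change computed from it omits the change during training. This assumes that section 3.2.1 was followed as written and that the scales are reported as change at all.

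Three stronger readings are tempting and unsupported:
- A reader might infer that technology gains are understated. The direction is unknown, so this cannot be claimed.
- A reader might infer that the secondary aim fails. Utilization data do not depend on this baseline, change after training remains interpretable if so named, and the primary feasibility and acceptability conclusions are untouched.
- A reader might infer that the collected data have this defect. The documents show a plan, not what was done.

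Nor does the small number of completers settle the severity. A systematic omission does not shrink with the sample. The point is minor because it concerns an uncontrolled, descriptive secondary aim in a pilot.

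A different defect should be kept apart. The footnote in section 3.2.2 that covers readiness, tablet opinions and the BADS reads "Pre and post only (i.e. not at 3, 6 or 9 weeks", while the schedule marks all three at week 9 and the BADS also at weeks 3 and 6. The WHODAS is footnoted as pre only but scheduled at weeks 9 and 12. That conflict has nothing to do with training order and needs its own reconciliation.

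**What to change.** **For further enrolment or a follow-on study:** change section 3.2.1 so that technology readiness, MDPQ-16 and tablet opinions are read aloud after consent and before Prism training begins, at the latest at the start of the training contact. This costs almost nothing, since it only moves three scales within a contact that already takes place. If a value is wanted before a mailed tablet arrives, one short separate call is needed.

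**For data already collected,** which the SAP's wording suggests is the present position: check the study records for the actual order. Where baseline followed training, describe the result in the SAP and report as change from a post-training baseline. The cost is one record check and one sentence in each document.

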3.2.2 Questionnaires

Questionnaires collected during the baseline and study assessments include (attached to IRB application):

1. Hamilton Depression Rating Scale (HAMD) for depression severity
2. Behavioral Activation for Depression Scale (BADS) for behavioral activation*
3. Duke social interaction subscale – to assess social connection
4. Duke perceived support subscale – to assess perceived social support
5. UCLA 3-item scale – to assess loneliness
6. 12-item World Health Organization Disability Assessment Schedule (WHODAS 2.0)- to assess different domains of disability**

7. Technology readiness questionnaire (Jay & Willis, 1992)*
8. Mobile Device Proficiency Scale (MDPQ-16)
9. Computer tablet opinions questionnaire (Czaja et al., 2018)*
10. Demographics**
11. Client Satisfaction Questionnaire 3-item for therapy satisfaction
12. Intent to Participate – to assess intention to continue study

*Pre and post only (i.e. not at 3, 6 or 9 weeks)

**Pre only

3.2.3. Engage therapy sessions

Participants will complete **9 Engage therapy sessions**. Engage is a form of personalized, stepwise treatment for late-life depression. The main intervention of Engage is an adapted form of behavioral activation tailored to older adults focused on “reward exposure,” namely encouraging patients to engage in (i.e., expose themselves to) rewarding activities between sessions to enhance activation of the reward system. At each session, patients will be guided to select a rewarding activity they had not engaged in recently or wanted to do more often. Then, the clinician will help patients develop a plan to engage in the selected activity and to cope with potential difficulties when exposed to such rewarding situations. If a patient does not successfully engage in planned rewarding activities and show clinical improvement by the third session, the clinician will add techniques to address barriers to reward exposure (Solomonov et al, 2019). Weekly depression severity is tracked using the PHQ-9. Engage has previously demonstrated efficacy for decreasing depressive symptoms in older adults ([name] et al, 2016).

3.2.4. Prism system

Throughout the **12-week study**, participants will be given the Prism 2.0 system to use. Participants will be provided a tablet with internet access, pre-loaded with the Prism 2.0 software. The Prism software involves a suite of programs for improving the social support and interaction felt by older adults. Previous studies have demonstrated that Prism system reduces loneliness and increases perceived social support and computer proficiency (Czaja et al., 2017). Prism software includes: Internet browser access (with vetted links to sites such as NIHSeniorHealth.Gov), an annotated resource guide, a dynamic classroom feature, a calendar, a photo feature, E-mail, games, and online help. Clinicians will incorporate elements of the Prism system into therapy as appropriate, and participants will be instructed to use the Prism system at their leisure or as it pertains to their chosen “reward exposure” activities.

3.2.5 Post-study interviews

Following completion of week 9 questionnaires, participants will discuss semi-structured interview questions with a study team member related to barriers and facilitators to the Engage therapy and use of the Prism technology platform (script attached). Interviews will be audio recorded with the consent of the participant.

4. Study Design

4.1 Study Population

The study population involves socially isolated/lonely older adult case management clients who endorse depressive symptoms.

4.2 Inclusion Criteria

Criteria Referral to study:

1. Age at least 60 years.
2. English speaking.
3. Currently enrolled in case management at in 2 included agencies
4. Major depression on the SCID and 24-item Hamilton Depression Rating Scale (HAM-D) ≥ 19
5. Report of loneliness social isolation as determined by the UCLA 3-item scale and Duke social interaction subscale, respectively

Following referral, participants must be willing and able to consent to the study procedures and related activities.

4.3 Exclusion Criteria

1. Psychotic depression by SCID-V, i.e. presence of delusions
2. High suicide risk, i.e. intent or plan to attempt suicide in the near future
3. Presence of any Axis I psychiatric disorder or substance abuse other than unipolar major depression
4. History of psychiatric disorders, hypomania, are excluded
5. Acute or severe medical illness, i.e. delirium, metastatic cancer, decompensated cardiac, liver, or kidney failure, major surgery, stroke, or myocardial infarction during the three months prior to entry; or drugs often causing depression, e.g. steroids, reserpine, alpha-methyl-dopa, tamoxiphen, vincristine
6. Current involvement in psychotherapy
7. Cognitive impairment (i.e. telephone administered MoCA < 11)
8. Currently dwelling in non-community dwelling (e.g. prison, nursing home)
9. Hearing that would not allow participants to complete sessions with the RA/therapist
10. Vision impairment that would not allow the participant to use the study provided tablet
11. Inability to speak English
12. Aphasia interfering with communication
13. Literacy – assessed by reading a paragraph designed for those at 6th grade reading level

INSTRUMENTS	Administered by:	Screening	Baseline	Wk 3	Wk 6	Wk 9	Wk 12
Screening Assessment							
Demographic Questionnaire	Research Assistant (RA)	X	X				
Medication List	RA	X					
Health Information Questionnaire	RA	X					
Functional status (WHODAS 12-item)	RA		X			X	X
Telephone- MoCa	RA	X					
Dx, Depression Severity and Anhedonia							
Hamilton Depression Rating Scale (HAMD)	Research Assistant	X	X	X	X	X	X
Structured Clinical Interview for DSM -V	Clinician	X					
SCID Score Sheet	RA	X					
PHQ-9	Clinician						Weekly during clinician sessions
Behavioral Activation							
Behavioral Activation for Depression Scale (BADS)	RA		X	X	X	X	X
Social Connection and Loneliness							
Duke (social interaction and perceived support subscales)	RA		X	X	X	X	X
UCLA Loneliness Scale 3-item	RA		X	X	X	X	X
Technology							
Technology readiness questionnaire	RA		X			X	
Mobile Device Proficiency Scale (MDPQ-16)	RA		X			X	X
Computer Tablet Opinions Questionnaire	RA		X			X	
Other							
Client Satisfaction Questionnaire 3-item	RA			X	X	X	X

Intent to Participate	RA		X	X	X	X	

